3.2.4 Pharmacokinetic (PK) Analysis Set

PK analysis set: the approximately 30 randomized participants who successfully received the study treatment on Day 1 and have specific post-Day 1 PK assessments.

3.3 Subject Data and Study Conduct

Data will be listed by site and subject.

3.3.1 Subject Disposition

The number and percentage of subjects in each of the following categories will be presented by treatment and in total for all screened subjects:

- Screened (only in the total column),
- Randomized (used as denominator when calculating the percentages for the following items),
- Successfully received the study treatment (LYR-210 or control) on Day 1,

- Completed the treatment phase,
- Early terminated the study treatment,
- Primary reasons for discontinuation of study treatment.

In addition, the number and percentage of subjects who discontinued study treatment due to COVID-19 will also be presented.

3.3.2 Protocol Deviations

Counts and percentages of subjects with CSR reportable protocol deviations by deviation category will be summarized by treatment and in total based on ITT Analysis Set.

3.3.3 Analysis Populations

Counts and percentages of subjects in each analysis set will be summarized by treatment and in total based on ITT Analysis Set. Reasons for exclusion from PP analysis Set will also be summarized.

3.3.4 Demographic and Baseline Characteristics

The following demographic and baseline characteristics will be summarized:

- Age (years) and age categories (<65 years, \geq 65 years)
- Sex
- Childbearing potential
- Region (North America vs Europe)
- Race
- Ethnicity
- Height (cm)
- Weight (kg)
- Body mass index (BMI) (kg/m²) and BMI categories (<30 kg/m², \geq 30 kg/m²)
- Randomized nasal polys status (with or without nasal polys)
- Actual nasal polys status (with or without nasal polys)

Demographic and baseline characteristics will be summarized with descriptive statistics or counts and percentages of subjects as appropriate by treatment and in total for ITT Analysis Set, ITT Analysis Set without nasal polyp, and Safety Analysis Set.

3.3.5 Chronic Rhinosinusitis History

The following baseline disease characteristics for chronic rhinosinusitis will be summarized by treatment group and in total for the ITT Analysis Set and ITT Analysis Set without nasal polyp:

- Time from diagnosis of CRS (years)
- Time from diagnosis of CRS (years) is calculated as (date of informed consent – date of diagnosis + 1)/365.25 if the dates are full; (month difference of date of informed consent and date of diagnosis)/12 if only day is missing; year difference of date of informed consent and date of diagnosis if both month and day are missing.
- Asthma status (yes or no)
- Perennial Allergic Rhinitis (yes or no or unknown)
- Seasonal Allergic Rhinitis (yes or no or unknown)
- Chronic Obstructive Pulmonary Disease (COPD) (yes or no)
- Smoking History (never, current, and former)

- Sensitive to nonsteroidal anti-inflammatory drugs (yes or no)
- Current or history of medication related to CRS:
 - Intranasal corticosteroid spray
 - Oral corticosteroids
 - Antibiotics
 - Saline irrigation
 - Other medication

3.3.6 Chronic Rhinosinusitis Surgical History

The following baseline disease characteristics for chronic rhinosinusitis surgery will be summarized by treatment group and in total for the ITT Analysis Set and ITT Analysis Set without nasal polyp:

- Septoplasty (yes or no)
- Nasal surgery involving turbinates (yes or no)
- Sinuplasty (yes or no)
- Polypectomy (yes or no)
- Facial Trauma (yes or no)

3.3.7 Medical History

Medical history (non-chronic rhinosinusitis medical/surgical history) will be coded using the Medical Dictionary for Regulatory Activities (MedDRA) version 24.1 (or later version). Counts and percentages of subjects with medical history by primary system organ class and preferred term will be summarized by treatment and in total for ITT Analysis Set and ITT Analysis Set without nasal polyp.

3.3.8 Concomitant Medications and Procedures

Concomitant medications will be coded to anatomical therapeutic chemical (ATC) class and preferred term using the WHO Drug Dictionary version B3 Global, Sep2021 (or later version). For summary purposes, medications will be considered prior medications if they stopped prior to the first dose of study drug and concomitant medications if they were taken at any time after the first dose of study drug but no later than 31 days (>31 days) after discontinuation of study treatment. Medications that started prior to the first insertion of study treatment and continued while study treatment was given will be counted in both prior and concomitant medications. Medications stopping on the same day as study treatment administration will be considered as concomitant medications.

If a medication has incomplete start or stop dates, dates will be imputed to determine whether a medication should be considered prior medication or concomitant medication based on the rules in Section 3.1.8.1.

Incomplete start and stop dates will be listed as collected without imputation.

Counts and percentages of subjects taking prior and concomitant medications by ATC class and preferred name will be summarized by treatment and in total for the ITT Analysis Set and ITT Analysis Set without nasal polyp.

3.3.9 Study Drug Exposure (Up to Matrices Removal or Dislodgement) and Compliance

Days of exposure to study drug will be calculated from the date of study treatment (LYR-210 or sham) administration. Days of exposure to study drug will be summarized by treatment and in total for the ITT Analysis Set with descriptive statistics and with counts and percentages of subjects with exposure in the following categories:

- <4 weeks (1 - 28 days)
- 4 - <8 weeks (29 - 56 days)
- 8 - <12 weeks (57 - 84 days)
- 12 - <16 weeks (85 - 112 days)
- 16 - <18 weeks (113 - 126 days)
- 18 - <20 weeks (127 - 140 days)
- 20 - <22 weeks (141 - 154 days)
- 22 - <24 weeks (155 - 168 days)
- 24 - <26 weeks (169 – 182 days)
- ≥26 weeks (≥183 days)

Compliance to the study drug regimen will not be calculated.

The LYR-210 administration/Sham procedure will be summarized by treatment and in total for all randomized subjects for the following items:

- Pre-procedure endoscopy performed
- Topical anesthesia applied before endoscopy
- Topical decongestant sprays applied before endoscopy
- Pre-procedure endoscopy assessments
 - Septal Deviation
 - Nasal Polyps
 - Concha Bullosa
- Was bilateral insertion procedure successful

3.4 Efficacy Analysis

The data derivation is described in Section 3.1.4. This Section will focus on the analysis and output.

Hypothesis testing for all efficacy endpoints will be conducted on the ITT Analysis Set with 2-sided testing and present a 2-sided 95% CI. For subjects with nasal polyp status is different from the IRT and eCRF, the polyp status that is recorded on Day 1 before the insertion procedure in the eCRF will be used.

Efficacy data will be summarized by treatment based on the ITT Analysis Set. The primary efficacy endpoint will also be summarized based on the PP Analysis Set.

Efficacy data will be listed by site and subject.

3.4.1 Primary Efficacy Endpoints

The primary objective is to evaluate the efficacy of LYR-210, compared with a sham procedure control, in improving the 3 cardinal symptoms of CRS in CRS participants without nasal polyps, who had previously failed medical management.

The key attributes of the estimand are as following (ICH E9(R1) (FDA 2021)¹):

Treatment LYR-210 7500 µg drug matrix over a 20-week period or sham procedure, with daily saline nasal irrigation

Population adults with CRS who do not have nasal polyps at baseline, have failed medical management (including treatment with intranasal corticosteroid sprays [INCS]), and have not had endoscopic sinus surgery (ESS)

Variable CFBL in the 7-day average composite score of the 3 cardinal symptoms (3CS) of nasal blockage/obstruction/congestion, anterior/posterior nasal discharge, and facial pain/pressure at Week 24

Population-level summary the difference in the mean change from baseline at Week 24 in the 3CS score between LYR-210 and sham

Analysis model mixed model with repeated measures (MMRM) model will include the fixed, categorical effects of treatment, visit, treatment-by-visit interaction, and nasal polyp stratum as well as covariates of baseline score and baseline score-by-visit interaction.

Intercurrent events (ICE) and strategy the intercurrent events (ICEs) by category and the corresponding strategies for addressing these ICEs are listed in

If both Category 1 ICE and Category 2 ICE occur for the same subject, the Category 1 ICE takes precedence over Category 2 ICE. For example, if a subject took rescue medication at Week 10, and subsequently dropped out at Week 12 with no 3CS score at Week 24, then the method addressing Category 1 ICE will be used.

Table 5. ICEs by Category and Strategies for Addressing ICEs in the Primary Estimand

Category 1 ICE: SCS use or ESS between baseline and Week 24	Category 2 ICE: Decongestants use or INCS use or early termination of study treatment due to any reasons (e.g., spontaneous bilateral matrix dislodgement of LYR-210)	Category 3 ICE: Infection with COVID-19
Composite Variable Strategy: The 3CS score post SCS use or ESS will be censored and imputed with the participant's post-baseline worst observed score.	Treatment Policy Strategy: The 3CS scores reported by the participants will be used regardless of whether the ICE occurs.	Hypothetical Strategy: The 3CS score reported by the participants post the ICE will be censored as if the COVID-19 infection did not occur.

Sensitivity analyses for the primary endpoints with various supplementary estimands such as treatment policy strategy will be conducted as specified in Section 3.4.1.3 to assess the robustness of the primary analysis.

3.4.1.1 Primary Analysis Method

The primary analysis to test difference between LYR-210 and sham in the mean change from baseline in 3CS score at week 24 will be performed on the ITT Analysis Set without nasal polyp using a mixed model with repeated measures (MMRM).

The MMRM will use change from baseline as the dependent variable, and include the fixed, categorical effects of treatment, visit, treatment-by-visit interaction, and covariates of baseline score and baseline score-by-visit interaction. An unstructured covariance structure shared across treatment groups will be used to model the within-subject errors. The covariance parameters in the above model will be fitted through a working model that assumes joint multivariate normality (MVN) of responses by maximizing the restricted likelihood (REML) under the working model, and the mean parameters will be estimated by generalized least squares after plugging in REML estimate of covariance parameters. In case the model does not converge with the unstructured covariance structure, the heterogenous Toeplitz structure (TOEPH) will be used instead. In case the model will not converge with the TOEPH structure, heterogenous compound symmetry (CSH) will be used instead. The Kenward-Roger approximation will be used to estimate denominator degrees of freedom and adjust nominal standard errors based on the inverse observed information from the working MVN model. Missing data will be handled by the MMRM under the missing at random (MAR) assumption. The impact of this assumption will be evaluated by sensitivity analyses specified in Section 3.4.1.2.

Least-squares means (LS-means) for change from baseline at each analysis visit will be provided for each treatment group and the difference in LS means between LYR-210 and sham treatment at each analysis visit, corresponding standard error, two-sided 95% confidence intervals and two-tailed p-value will be estimated from the MMRM model.

Descriptive summary statistics on the values and changes from baseline will be presented for the 3CS score at each analysis visit by treatment group.

Graphic displays of the results will be presented. The by-visit means and the standard errors for each treatment will be plotted by the analysis visit. In addition, the by-visit least squares mean changes and the standard errors for each treatment will also be plotted by the analysis visit.

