9.3.2 Analysis methods

Data collected in this study will be presented using listings, summary tables, and figures. Continuous data will be summarized by treatment group using the following descriptive statistics: the number of observations (n), mean, SD, median, minimum, and maximum. Categorical data will be summarized by treatment group as number and percentage of participants in each category. Individual participant's data will be presented in listings.

For cardinal symptoms (3CS and individual symptoms), the baseline score is the average of nonmissing daily scores over the 7-day period prior to and including Day 1. For other efficacy and safety assessments, the baseline value is the last nonmissing value prior to treatment administration.

Unless otherwise specified, all hypothesis tests will be conducted at a 2-sided significance level of 0.05 and all confidence intervals will be constructed 2-sided with a confidence level of 95%.

The primary analysis method for the primary endpoint will be a mixed models repeated measures analysis of covariance (MMRM) with treatment group, week and nasal polyp status (grade 1 polyp vs no polyp) as factors, with baseline measurement as covariate, an interaction of

treatment by week and an interaction of baseline measurement by week. The primary analysis will be conducted according to the primary estimand that is specified in Table 1. Sensitivity analysis will be conducted to assess the impact of the missing at random assumption in the MMRM. Additionally, supplemental analyses will be conducted to assess the robustness of the primary analysis according to the prespecified plan in the SAP. The LS mean change for each treatment group, the LS mean difference between treatment groups, as well as the corresponding 95% confidence intervals and p-values will be reported.

Changes from baseline to continuous endpoints will be analyzed using an MMRM or ANCOVA as appropriate which will be prespecified in the SAP.

Time-to-event endpoints will be analyzed using the Kaplan-Meier (K-M) method. The K-M curves will be compared between treatment groups using the log-rank test.

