9.3.7 Efficacy analyses

Hypothesis testing for all efficacy endpoints will be conducted on the ITT population. The study level type-1 error for the family of primary and key secondary efficacy hypotheses will be controlled at alpha of 0.05. Unless otherwise noted, all analyses of efficacy outcome measures will be adjusted for baseline score, geographic region, and nasal polyp status. Adjustment by additional covariates, if any, will be described in the SAP.

All efficacy analyses will be carried out after the last participant completes the blinded Week 24 visit or withdraws prematurely before Week 24, and all data from the 24-week study period have been entered into the study database, cleaned, verified, and locked.

Efficacy data collected during the safety extension phase will be summarized descriptively.

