2.2.2 Randomization and Blinding

On Day 1, after confirmation of eligibility and baseline assessments, and before any treatment, participants will be randomized in a 2:1 ratio to receive LYR-210 treatment or control (sham procedure) with stratification based on region (North America vs Europe) and nasal polyp status (yes vs no). Randomization will be conducted using Interactive Response Technology (IRT) and treatment will be assigned according to a randomization scheme generated by an unblinded biostatistician. The person generating the randomization scheme will not be involved in the collection, review, and/or analysis of study data before database lock and unblinding of the database.

To maintain the participant blind to treatment assignment, each participant will wear an eye mask (i.e., blindfold) and headphones at the time of the LYR-210 administration/sham procedure. Except for the cases of spontaneous matrix dislodgement, participants should remain blinded to their treatment assignment (LYR-210 or control) until the study is completed.

After Week 24, using IRT, control participants will be assigned to active treatment and treatment participants will be re-randomized 1:1 to either sham procedure or a second active treatment procedure stratified by geographic region and nasal polyp status at baseline. Follow-up visits will continue through Week 52.

The sponsor will be blinded to participants' initial study treatment assignments until database lock for the Week 24 primary analysis (initial randomized phase).

Due to the nature of the procedure, the treating investigator/surgeon will not be blinded to the treatment assignment. Efforts will be made to keep the study coordinator and other study staff blinded.

Breaking the blind to the participant is expressly forbidden except in the event of spontaneous dislodgment of LYR-210, or a medical emergency where the identity of the treatment assignment must be known to properly treat the participant. If breaking the blind is required because of a medical emergency, decision to unblind lies solely with the investigator. In all cases where the blind is broken to the participant, the investigator must record the date and reason for breaking the blind. The unblinding should be noted in the participant's electronic case report form (eCRF).

Every effort will be made to maintain the integrity of the study while conducting the 24-week analysis.

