3.4.2 Key Secondary Efficacy Endpoints

The estimand attributes for the following key secondary efficacy endpoints are defined in the same manner as for primary efficacy endpoint in Section 3.4.1:

1. CFBL in the 7-day average composite score of 3CS at Week 24 in all participants.

2. CFBL in the 22-item Sino-Nasal Outcome Test (SNOT-22) total score at Week 24 in all participants.

The same analysis methods used for the primary efficacy endpoint will be used for the above key secondary efficacy endpoints by including an additional term for polyp status as a stratum. The LS-means for change from baseline at each analysis visit will be provided for each treatment group and the difference between LYR-210 and sham treatment at each analysis visit will be estimated along with the CIs. The p-value for the comparison at each analysis visit will also be presented.

3. CFBL in the percent opacification of the bilateral anterior and posterior ethmoids at Week 20 as determined by 3-D volumetric CT analysis in all participants.

The above endpoints will be analyzed by ANCOVA with fixed-effect terms for treatment group and nasal polyp status. LS-means in each treatment group and their difference with 95% confidence interval (CI) and p-value will be provided.

4. Rescue treatment requirement through Week 24

Rescue treatment requirement through Week 24 will be summarized descriptively. Statistical comparisons between Lyra and Sham groups will be conducted on the pooled data with ENLIGHTEN 2 according to the integrated summary of efficacy SAP following the prespecified hierarchical testing method to adjust the multiplicity adjustment.

Descriptive summary statistics on the values and changes from baseline will be presented for the above key secondary efficacy endpoints at each analysis visit by treatment group.

In addition, the point estimate and the two-sided 95% exact binomial confidence intervals (using the Clopper-Pearson method) will be presented for the proportion of subjects requiring rescue treatment through Week 24 will be tabulated by treatment group in the ISE.

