5 CHANGES FROM PROTOCOL

There is no change from the protocol-specified statistical analyses.

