Appendix C

List of Changes in SAP Version 2.0 from Version 1.0

SAP Sections	Description	Rationale
3.4.1.1	Stratum Nasal Polyp is removed from the primary analysis model MMRM	Remove as the primary analysis population is the participants without nasal polyp.
3.4.3.1	Added sensitivity analysis with a treatment policy for ICE of SCS use and ESS	To incorporate treatment policy in consideration of FDA's feedback.
3.4.3.1	Added sensitivity analysis of composite strategy for ICE of SCS use and ESS for CRS indication and a treatment policy for SCS use for non-CRS indication.	To assess robustness of the primary estimand.
3.6.1	Added definition of treatment emergent AESI. Added summary measures for AESI and AEs leading to discontinuation, ie risk difference between the treatment groups and its 95% CI.	To incorporate FDA's feedback.

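### The primary MMRM and the MMRMs for key secondary endpoints 1 and 2 omit region, a stratification factor. The protocol is ambiguous on this for the primary test, and the cost is at most a small loss of precision.

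*SAP*

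**What the plan says.** **Design.** SAP 2.2.2 and Protocol 3.5.4 randomise 2:1 "with stratification based on region (North America vs Europe) and nasal polyp status (yes vs no").

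**Primary model in the SAP.** The primary analysis uses the ITT set without nasal polyps. Under SAP 3.4.1.1 the MMRM will "include the fixed, categorical effects of treatment, visit, treatment-by-visit interaction, and covariates of baseline score and baseline score-by-visit interaction". The model line in the estimand description (SAP 3.4.1) does not name region either. Appendix C records one change to the primary model: "Stratum Nasal Polyp is removed from the primary analysis model MMRM". That is reasonable in a population without polyps. Region is not mentioned.

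**Key secondaries 1 and 2 in the SAP.** SAP 3.4.2 reuses the primary method "by including an additional term for polyp status as a stratum". Region is again absent.

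**Protocol.** Section 9.3.7 gives the general rule: "Unless otherwise noted, all analyses of efficacy outcome measures will be adjusted for baseline score, geographic region, and nasal polyp status". Section 9.3.2 gives the primary MMRM as "treatment group, week and nasal polyp status (grade 1 polyp vs no polyp) as factors, with baseline measurement as covariate", plus two interactions with week. For other continuous endpoints, 9.3.2 leaves the choice of MMRM or ANCOVA to the SAP and lists no terms.

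**Declared changes.** SAP Section 5: "There is no change from the protocol-specified statistical analyses".

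**The concern.** Stratifying by region balances the arms within region, so the treatment difference varies less from one randomisation to the next to the extent that region predicts outcome. A model without region does not credit that gain: it leaves between-region variation in the residual and reports a standard error larger than the design produces. The confidence interval is then wider, and the p-value larger, than they need be.

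The second issue is specification. Whether the primary test is adjusted for region has two answers in the documents: yes by the default in Protocol 9.3.7, no by the model lists in Protocol 9.3.2 and SAP 3.4.1.1. The primary test is the gatekeeper of the testing hierarchy in SAP 3.1.7. If its p-value fell near 0.05, either model could be argued for after unblinding.

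**Working it through.** **1. Reproduce the plan's figure.** SAP 2.2.4 gives 50 control and 100 LYR-210 participants, two-sided alpha 0.05, effect size 0.63, difference 1.31 and power 0.95.

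- Implied SD = 1.31 / 0.63 = 2.08.
- SE of the difference = 2.08 × √(1/50 + 1/100) = 0.360, and 1.31 / 0.360 = 3.64.
- Power = 0.953 (normal) or 0.951 (noncentral t, 148 df).

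The stated 0.95 reproduces. The sample size uses no region term and is not in error.

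**2. Assumptions.** The documents give neither the regional split nor any regional difference in 3CS change. Assumed:

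- a contrast δ of 0, 0.5 or 1.0 points between regions, read as what remains after baseline adjustment;
- a share p in one region of 0.5 or 0.7;
- total SD held at 2.08.

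**3. Formulas.**

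- Share of variance due to region: R² = p(1 − p)δ² / SD².
- Overstatement of the SE when region is omitted: 1/√(1 − R²) − 1.
- True size of the nominal 0.05 test: 2 × P(T > 1.976/√(1 − R²)), T on 148 df.
- Power at 1.31: true SE = 0.360 × √(1 − R²). The model without region tests against 0.360; the model with region tests against the true SE. Power below uses the normal approximation.

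Worked case, p = 0.5 and δ = 1.0: R² = 0.25 × 1.0 / 4.32 = 0.058; 1/√0.942 = 1.030; critical value 1.976 × 1.030 = 2.036; size about 0.044.

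| Split | δ | R² | SE overstated | Size without region | Power at 1.31, without → with region |
|---|---|---|---|---|---|
| either | 0 | 0 | 0% | 0.050 | 0.953 → 0.953 |
| 70:30 | 0.5 | 0.012 | 0.6% | 0.049 | 0.954 → 0.955 |
| 50:50 | 0.5 | 0.014 | 0.7% | 0.048 | 0.954 → 0.956 |
| 70:30 | 1.0 | 0.049 | 2.5% | 0.045 | 0.957 → 0.962 |
| 50:50 | 1.0 | 0.058 | 3.0% | 0.044 | 0.958 → 0.963 |

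**4. Simulation check.** Permuted blocks 2:1 within region, n = 150, 50:50 split, linear model at one time point (20,000 runs for size, 10,000 for power):

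- δ = 0: size 0.051 without and with region; power 0.951 for both.
- δ = 0.5: size 0.049 without, 0.051 with; power 0.953 without, 0.954 with.
- δ = 1.0: size 0.042 without, 0.048 with; power 0.957 without, 0.964 with.

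This agrees with the table within simulation error. Neither calculation includes the baseline covariate or the repeated visits, so both approximate the MMRM.

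**5. Key secondaries.** For key secondary 1 the implied SD is 1.19 / 0.57 = 2.09, so the SE overstatement is almost the same for the same δ and split. The documents give no SD for SNOT-22, so key secondary 2 cannot be sized.

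**6. The text, endpoint by endpoint.**

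- *Primary:* Protocol 9.3.7 says adjust for region unless otherwise noted. Protocol 9.3.2 specifies the model without region and does not say whether it is an exception. The SAP matches 9.3.2.
- *Key secondaries 1 and 2:* Protocol 9.3.2 lists no terms, so the 9.3.7 default is the only protocol statement on covariates. The SAP leaves region out and notes no exception.
- *Responder endpoints, for context:* Protocol 9.3.2 names a CMH test controlling for region and polyp status. SAP 3.4.3 uses logistic regression with polyp status and baseline only.

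**The case against.** The strongest reply is that a specific model overrides a general rule. Protocol 9.3.7 carries an exception clause, and Protocol 9.3.2 sets out the primary model in full without region. On that reading the SAP follows the protocol for the primary test, and the no-change statement in SAP Section 5 is correct on this point. This stands. A reader might infer that the primary model breaks the protocol's adjustment rule; the documents support only an unresolved tension between 9.3.2 and 9.3.7. The reply is weaker for key secondaries 1 and 2, where 9.3.2 lists no terms and the SAP notes no exception.

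A reader might also infer that a standard error that ignores the stratification makes the primary test invalid. It does not. The treatment difference is not biased, and the test errs on the conservative side.

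Finally, the loss may be nil. It needs a regional difference that baseline does not already absorb, and the documents give no evidence of one. The upper assumed contrast of 1.0 is 76% of the design difference (1.0 / 1.31). This also stands, and it keeps the precision argument modest. What it does not answer is that the covariate set of the gatekeeping test should have one reading before unblinding, and that the default in 9.3.7 already names region.

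**Conclusion.** The point holds as a low-cost improvement and a consistency correction. Region is a stratification factor, it is the only one that varies in the primary population, and it is absent from the primary MMRM and from the MMRMs for key secondaries 1 and 2. For the primary test the protocol is ambiguous; for the two key secondaries the SAP drops the default adjustment without noting it.

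Under the assumed ranges the standard error is overstated by about 0.6% to 3.0%, the true size is about 0.049 to 0.044, and adding region gains about half a percentage point of power or less at 1.31. With no region effect, nothing material changes. These figures rest on the assumed contrast and split and on a single-time-point approximation. A substantial loss of power at the design difference cannot be claimed from these documents.

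**What to change.** Before the Week 24 database lock:

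- Add region as randomised (North America vs Europe) as a fixed effect in the primary MMRM (SAP 3.4.1.1) and in the MMRMs for key secondaries 1 and 2 (SAP 3.4.2). Align the model line in SAP 3.4.1.
- Make Protocol 9.3.2 and 9.3.7 agree on the covariates of the primary model.

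The cost is one degree of freedom per model and a wording change. SAP 1 places approval of Version 2.0 before that lock, so the change can be made while treatment assignments are still blinded. No data collection changes, because region is already recorded for randomisation.
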